1.1 Protocol Synopsis

- **Primary and Secondary objectives and endpoints**

- Primary Objective - To measure the impact of Complement Theory's Program on Quality of Life of cancer survivors as measured by FACT-G questionnaire.
- Secondary Objectives:
 - Quantify the effect of CT's program on employee absenteeism by tracking changes in the number of sick days taken by participants.
 - Determine the program's impact on employee presenteeism by assessing changes in work motivation and employee performance review scores.
- Exploratory Objective
 - To quantify the impact of Complement Theory's Program on total healthcare expenditure in cancer survivors.
 - Assess the impact of CT's Program on the progression and recurrence rates of prostate, colorectal, and lung cancers, by evaluating changes in tumor size and biomarker levels, including Blood pressure, PSA or protein, in addition to monitoring actual recurrence rates.

- **Overall Design**

- Several key aspects of the trial design are summarized below:

Trial Model	Randomized control trial with two parallel groups: one active comparator (control) and one test group.
Test Intervention	Live Coactive Coaching program, focusing on Exercise and Meditation, along with app-guided

	evidence-based information on Diet, Sleep, and other lifestyle practices for 48 weeks (12 months)
Active Comparator (Control)	48 weeks access to Digital application with expert guidelines on lifestyle modification focusing on exercise, meditation, as well as information on diet, sleep and other lifestyle practices. Does not include live coaching and personalization.
Trial Intervention Assignment Method	Randomization
Population Type	Adult survivor
Population Diagnosis	Active Cancer (Breast, Prostate, Colorectal, Lung and Other) Stage 1-4
Population Age	21 yrs and above
Site Distribution	Digital Recruitment of participants who can be anywhere in the US

- **Number of Arms**

- Two - One active comparator (control) and one test

- **Blinding**

- The study will be double-blind: Participants and the Principal Investigator will not be made aware of treatment assignment.
- Both the groups shall be given access to the app. The contents shall be different for active comparator and the test group.

- **No of Participants**

[figure not shown]
- 146 (73 Maximum to be assigned randomly each to control and treatment)

- **Arms and Duration**

- Treatment Group
 - Participants will get access to Complement Theory's 12 month Live Coactive Coaching program, focusing on Exercise and Meditation and supplemented with evidence-based information on Diet, Sleep, and other lifestyle practices, adjunct to the core treatment.
 - Each week, up to five sessions of 45 minutes each will be offered, with a recommendation for participants to engage in a minimum of three sessions to ensure adequate program exposure and benefits.
 - Each session will consist of 30 Minutes of Physical Exercise and 7 minutes of meditation. Each session will be a combination session focused on Aerobic and Strength, with flexibility and balance exercises included as supplements.
 - Participants will be allocated to Low / Moderate intensity programs based on their specific medical profile, ensuring that the exercises and meditation practices are safe, effective, and aligned with their health status and cancer treatment plan.
- Active Comparator (Control) Group
 - Participants in this group will receive access to a curated collection of publicly available guidelines for lifestyle modification. These resources, presented through a digital application, will focus on exercise, meditation, diet, and sleep, but without the live coaching or program personalization.
 - This comparison aims to evaluate the impact of personalized, interactive live Coactive coaching against self-guided learning using standard guidelines.
- The overall duration for an individual participant is anticipated to be 12 months for the active phase, with a 6 month follow-up period for long-term data collection.
- **Committees:**

- Throughout the study, safety oversight will be provided by the Trial Monitoring Committee (TMC), composed of oncologists, cancer exercise specialists and biostatisticians.
- All participants enrolled in the study will be included in the safety analysis. The Trial Monitoring Committee will be responsible for reviewing relevant safety findings related to study outcomes.

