2.1 Purpose of Trial

The randomized controlled trial (RCT) aims to evaluate the efficacy of Complement Theory's (CT) personalized and interactive, evidence-backed lifestyle program in reducing healthcare costs and improving health outcomes for survivors across all major cancer types.

Distinct from conventional interventions, CT's program offers live coactive coaching through a mobile app, concentrating on Exercise and Meditation, and is enriched with evidence-based advice on Diet, Sleep, and comprehensive lifestyle modifications. This trial is pivotal in assessing the program's effectiveness against an active comparator—expert-recommended lifestyle modification resources suitable for cancer survivors—to isolate the impact of coaching and personalization.

The primary objective is to investigate whether CT's novel approach can more effectively reduce healthcare utilization, through reduction of hospitalizations, urgent care visits, and outpatient visits. Furthermore, the trial seeks to measure adherence to treatment, and significant health outcomes, including improvements in Quality of Life Scores (QoLS) to

provide a holistic evaluation of the program's impact on patient care and well-being. As an exploratory effort, the trial will also measure cancer progression, recurrence in Prostate and Colorectal cancer survivors alone.

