 - Motivation to work: Assessed through self-reported scales or questionnaires.
 - Performance review scores: Obtained from employer records or self-reported performance evaluations.
- Estimand(s): The difference in mean scores of motivation and performance reviews between the intervention and control groups over the trial period.

Exploratory Objective(s):

Impact on rates of cancer progression, and recurrence

Clinical Question: What is the effect of Complement Theory's program on progression and recurrence of prostate, lung and colorectal cancers?

- Endpoint(s):
 - Cancer progression: Measured by changes in tumor size and changes in levels of biomarkers.
 - Recurrence: Incidence of cancer recurrence.
- Estimand(s): Directional trends evaluating the difference in proportions or rates of cancer progression and recurrence between the intervention and control groups during and post-trial follow-up.

Rationale for Excluding Breast Cancer from Exploratory Objective:

- Breast cancer, in particular, exhibits a longer average timeframe for recurrence when compared to prostate, lung and colorectal cancers. This longer latency could extend beyond the scope of our study's follow-up period, making it

challenging to accurately measure the program's impact on recurrence rates within the study's duration.

- By focusing on prostate, lung and colorectal cancers, we aim to assess the program's impact on cancers with more predictable progression patterns and well-established biomarkers, enabling a clearer evaluation of the Complement Theory's potential benefits in these specific cancer populations.

Impact on Total Healthcare Expenditure

Clinical Question: Does participation in Complement Theory's 12-month Live coactive Coaching program, focusing on Exercise and Meditation and supplemented with evidence-based information on Diet, Sleep, and other lifestyle practices, adjunct to the core treatment, lead to a reduction in total healthcare expenditure for cancer survivors?

- Endpoint(s): Total healthcare expenditure, including hospitalization costs, medication expenses, outpatient visits, and any other related healthcare services that we planned and unplanned, cancer and non-cancer, over the trial period.
- Estimand(s): The difference in mean total healthcare expenditure between the intervention and control groups over a specified period (e.g., at 12 months and 18 months from baseline).

3.1 Summary of objectives, endpoints and estimands:

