5.3 Inclusion Criteria

- Cancer Type : Breast, Prostate, Colorectal, Lung and Other Cancers
 - Other Cancers here refers all other cancer types apart from Breast, Prostate, Colorectal and Lung Cancer
- Cancer Stage: Stage 1 to 4
- Treatment Status: Has undergone any cancer-related treatment in last 12 months
- Age : 21 yrs and above
- Permission to access to last 1 year digital health records
- Access to smartphone or a tablet

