9.1 Analysis Sets

- The analysis will include the following datasets:
 - Intent-to-Treat (ITT) set: Including all randomized survivors, regardless of their adherence with the entry criteria. This set will be used for the primary analysis of Quality of Life changes and cancer progression.
 - Per-Protocol (PP) set: Including participants who completed the trial according to the protocol without significant deviations. PP set is a subset of ITT set, excluding survivors with major protocol deviations or those who do not complete the trial. This set will be used to summarize efficacy and support sensitivity analyses.

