9.1 Analysis Sets

- The analysis will include the following datasets:

- Intent-to-Treat (ITT) set: Including all randomized survivors, regardless of their adherence with the entry criteria. This set will be used for the primary analysis of healthcare expenditure reduction and cancer progression.
- Per-Protocol (PP) set: Including participants who completed the trial according to the protocol without significant deviations. PP set is a subset of ITT set, excluding survivors with major protocol deviations or those who do not complete the trial. This set will be used to summarize efficacy and support sensitivity analyses.

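### The exploratory recurrence and progression endpoints have no at-risk denominator, and 2.1, Section 3 and 9.1 disagree on which cancers they cover

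*Protocol*

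**What the plan says.** **Who enrols.** The Protocol synopsis (1.1) calls the population type "Adult survivor" and the diagnosis "Active Cancer (Breast, Prostate, Colorectal, Lung and Other) Stage 1-4". The criteria in 5.3 ask for any cancer type, Stage 1 to 4, and "Has undergone any cancer-related treatment in last 12 months". Neither 5.3 nor 5.4 asks for active or measurable disease, or for its absence.

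**What is measured.** Under its exploratory objective, Section 3 defines progression through change in tumor size and in biomarker levels, and gives the other endpoint as "Recurrence: Incidence of cancer recurrence". The estimand is a directional comparison of proportions or rates between the two arms. It is not restricted by disease status at entry.

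**In which cancers.** Section 3 names prostate, lung and colorectal cancer and gives a written reason for leaving out breast. Section 2.1 says "the trial will also measure cancer progression, recurrence in Prostate and Colorectal cancer survivors alone". Section 9.1 defines the ITT set as everyone randomized and states: "This set will be used for the primary analysis of Quality of Life changes and cancer progression". In the Combined protocol and SAP, 9.1 does the same: "This set will be used for the primary analysis of healthcare expenditure reduction and cancer progression".

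**What is known at baseline.** Section 8.1, item 4, collects survivor-reported disease assessments to describe baseline disease status. No analysis section uses them.

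**The concern.** Recurrence can be observed only in someone who is disease-free at the start. A change in tumor size can be observed only in someone with a tumor. If both kinds of participant enrol and each endpoint is expressed per randomized arm, each rate has people in its denominator who could not have had the event. The rate then depends partly on the case mix at entry. Randomization uses cancer type alone (6.6), so the disease-free share is left to chance within each cancer type.

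Separately, an analyst who follows 9.1 on progression would include breast and other cancers, which Section 3 deliberately leaves out. An analyst who follows 2.1 would drop lung. Three analysts could report three different results, each with a section of the Protocol to cite. At stake is whether the exploratory recurrence and progression results can be interpreted.

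**Working it through.** **1. Can disease-free people enrol?** Section 5.2 counts surgery alone as qualifying treatment. Section 5.4 excludes surgery only within four weeks either side of entry. Someone with a Stage 1 tumor fully resected 11 months ago, and otherwise eligible, therefore meets 5.3 and 5.4. (Section 5.2 gives a treatment window of six months where 5.3 gives 12; the same holds for a resection five months ago.) So the criteria admit a mix, although the synopsis line alone would not suggest one.

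**2. Cancer scope, side by side (Protocol).**

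| Section | Endpoint | Cancers |
|---|---|---|
| 1.1, 3, 3.1, 4.2 | progression and recurrence | prostate, lung, colorectal |
| 2.1 | progression and recurrence | prostate, colorectal |
| 9.1 | progression (recurrence not named) | all randomized, so also breast and other |

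**3. The plan's own figure.** Section 9.7 gives recurrence 0.30 (control) and 0.21 (test), a spread of 10%, one-sided alpha 0.05, power 80%, and 32 participants. With 0.10 used as a standard deviation:

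n per arm = 2 × 0.10² × (1.645 + 0.842)² / 0.09² = 15.3, rounded up to 16, so 32 in total.

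The figure reproduces as a comparison of means of a continuous score. No at-risk share enters it. Compared as two proportions, 0.30 against 0.21 needs 289 per arm (one-sided).

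**4. Dilution.** Assume that 0.30 and 0.21 are rates among people at risk, that a share p of those analysed is at risk, and that the rest contribute no events. The difference is then 0.30p − 0.21p = 0.09p:

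- p = 0.7: 0.063
- p = 0.5: 0.045
- p = 0.3: 0.027

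The ratio stays at 0.21/0.30 = 0.70 for every p. The documents do not give p.

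**5. Does restricting the denominator recover power?** For two proportions, one-sided:

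power = Φ[(Δ − 1.645 × se0) / se1], with se0 = √(2p̄(1 − p̄)/n) and se1 = √((p1(1 − p1) + p2(1 − p2))/n), where p1 and p2 are the two event rates and p̄ is their mean.

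At n = 73 and p = 1, se0 = 0.0721 and se1 = 0.0718, so power = Φ(−0.40) = 34.5%.

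| p (assumed) | At risk per arm | Power, at-risk set | Difference, all 73 per arm | Power, all 73 per arm |
|---|---|---|---|---|
| 0.2 | 15 | 13.9% | 0.018 | 12.5% |
| 0.3 | 22 | 16.7% | 0.027 | 15.1% |
| 0.4 | 29 | 19.4% | 0.036 | 17.7% |
| 0.6 | 44 | 24.8% | 0.054 | 22.9% |
| 0.8 | 58 | 29.6% | 0.072 | 28.5% |
| 1.0 | 73 | 34.5% | 0.090 | 34.5% |

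The largest gain is 24.8 − 22.9 = 1.9 points.

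**6. Chance imbalance.** Suppose the program has no effect and the rate among those at risk is 0.30. Disease-free shares of 0.6 and 0.4 then give 0.18 and 0.12, a difference of 0.06, or 0.06/0.09 = 67% of the planned effect. If the true share is 0.5 in both arms, the exact binomial probability of a gap of 20 points or more, in either direction, is 1.6% at 73 per arm, 3.7% at 51, and about 16% at an assumed 30 per arm in the three-cancer subset. A gap of 10 points or more has probability 21% at 73 per arm. A gap of exactly 10 points gives 0.30 × 0.10 = 0.03, one-third of the planned effect.

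**The case against.** Several stronger readings are tempting, and the documents do not support them.

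- **That the plan counts recurrence in everyone randomized.** Section 9.1 names progression only, and 9.2 and 9.3 give no analysis for either endpoint. Whole-arm recurrence rates are an inference from the Section 3 estimand.
- **That breast cancer is deliberately brought back.** The three-cancer scope appears in 1.1, 3, 3.1 and 4.2. Section 9.1 can be read as all randomized participants within that scope. This is an unresolved contradiction rather than a stated plan.
- **That nobody in the synopsis population can recur.** This needs a strict reading of the word Active. The same synopsis says "Adult survivor" and plans to monitor recurrence, and 6.8 describes the program as given alongside cancer treatment. Active may mean under or near treatment.
- **That disease-free people cannot contribute to progression.** This is true of tumor size but not of biomarkers. PSA is named in the synopsis and can be measured without a measurable tumor.
- **That the results will be seriously biased.** The 0.6 against 0.4 split is an unlikely draw at full size. Such imbalance is chance variation under randomization, which an ordinary standard error covers.

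Two further objections stand. Section 9.7 does not say that 0.30 and 0.21 are rates among disease-free people; if they are whole-group rates, 0.09 is already the whole-arm difference and the dilution in step 4 does not apply. And the baseline data are less ready than they look: 8.1 item 4 lists examples and specifies no disease-free or active classification, and the Cancer Progression Status row in 6.1 has no baseline mark.

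What remains is that the criteria admit both groups, neither endpoint has a defined at-risk set, and the sections disagree on cancer types.

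**Conclusion.** The point holds as a defect in how two exploratory endpoints are defined. The synopsis and 5.3 differ on disease status, Section 3 gives no at-risk denominator, and 2.1, Section 3 and 9.1 give three different scopes. On the assumption stated in step 4, the planned recurrence difference of 0.09 would appear as 0.027 to 0.063 for p between 0.3 and 0.7, with the ratio unchanged.

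The consequence is limited to interpretability. In the Protocol, the FACT-G primary analysis and the secondary analyses are untouched. In both documents the requirement of 102 comes from employee performance and total expenditure, so the sample size does not move. Clean denominators would not make the endpoints well powered. They still matter, because the plan intends to read only the direction of these results and gives no formal test against which to judge a shift caused by case mix.

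**What to change.** 1. Reconcile the synopsis with 5.3 on disease status, so that one description of the population holds throughout.
2. Make 2.1 and 9.1 agree with Section 3 on cancer types, in both documents.
3. In 9.1, replace the assignment of progression to the full ITT set with exploratory sets, analysed by randomized arm within the Section 3 cancers and defined from the baseline assessment in 8.1 item 4:
   - recurrence among those disease-free at baseline;
   - tumor-size progression among those with active or measurable disease at baseline;
   - biomarker change among those with a baseline biomarker value, reported separately by baseline disease status.
4. Report the number at risk per arm beside every rate.

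Because the sets are fixed by baseline information, the comparison between randomized arms is kept. Most of the cost is wording, with no added participants or visits. The baseline form may need one explicit item that classifies disease status. The downsides are smaller exploratory denominators and a baseline status that rests on survivor report.

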4.1 Description of Trial Design

- **Description of Intervention Model**

- This randomized control trial features two parallel groups: an active comparator (control) group and a treatment group, aiming for a total of 146 participants diagnosed with one of the following cancers - Breast, Colorectal, Prostate Lung and Other Cancer.

- The treatment group will be given live coactive coaching and personalized digital application program focused on Exercise and Meditation, supplemented with evidence-based facts on Diet, Sleep, and other lifestyle practices
- On the other hand, the control group will be given a digital application with expert guidelines on lifestyle modification, available publicly but with no live coaching and personalization.
- In essence, this is a superiority trial aimed at establishing that CT's program is more effective in improving outcomes.

- **Description of Trial Duration**

- The overall duration for an individual participant is anticipated to be 48 weeks (minimum 3, up to 5 days per week, 45 mins each session) for the active phase, with a 6 month follow-up period for long-term data collection.
- This duration allows for a comprehensive assessment of the intervention's immediate and sustained impacts on health outcomes and healthcare costs.

- **Method of Assignment to Trial Intervention**

- Participants in each group will be recruited transparently through online advertisements while ensuring balanced representation across cancer types.
- Blinding: The participants will not be aware if they are in control or test group.
- Number of Arms: Two – one control and one treatment group.

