6.3 Dosing and Administration

Details for Trial Intervention (Test Group):

- Timing of Intervention: Participants can log in at their convenience, with the flexibility to schedule exercise coaching sessions according to their preferences and availability.
- Intervention Structure: Over the course of 12-months or 48 weeks, each participant will participate in 3-5 weekly live sessions. Each session, spanning approximately 45 minutes, combines 30 minutes of targeted exercise with 7 minutes of meditation. Each session will be supervised live by a coactive coach for each participant. The program is strategically developed to progressively escalate in intensity:
 - Each session will consist of an optimal combination of Aerobic and Strength exercises.
 - Flexibility and Balance exercises will be included as supplemental exercises in the sessions.

12 Months Program Structure

Months 1 and 2

- Initially participants will be given 1:1 coaching to ensure that the participants get immediate feedback as well as modifications as needed.
- 10 workouts will be presented to the participants in Month 1 and 2. Each workout will be repeated 4 times, hence completing 40 days of workouts.
- The first 2 weeks will be “Light”: allowing the participants to complete the 10 workouts in flow while building confidence without pushing too hard or feeling too sore.
- The second 2 weeks will be “Light/Moderate”: allowing the participant to repeat the same 10 workouts, feel more confident in their ability to finish each workout because they are not brand new, but also experience a slight challenge on the body with the order in which the workouts are laid out.
- The third 2 weeks will be “Moderate”: the participants are expected to begin to feel stronger and more capable at this point which allows them to push a little harder and enjoy the challenge without burnout.
- The fourth 2 weeks will be “Moderate/Hard”: the participant by now should be experiencing what it’s like for the body to master the foundational goals above.

Month 3, 4, 5 and 6

- Next set of 10 workouts will be introduced in months 3 and 4, and likewise in months 5 and 6.

Month 6 to 12

- Based on their ability and progress, participants will be slowly graduated from 1:1 coactive sessions to Group-coactive sessions.

- Planned Route of Administration: The intervention will be administered remotely via the online platform, accessible through mobile devices.

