6.6 Participant Recruitment, Randomization and Blinding

- **Participant Recruitment**

- Participants will be recruited through a unified online advertisement campaign across platforms such as Facebook and Google. Interested individuals will click on the advertisement, which directs them to a screening form where they provide preliminary information relevant to the study eligibility criteria.

- **Randomization**

- Screening and Eligibility Confirmation: Upon submission of the screening form, potential participants will undergo an initial eligibility assessment based on predefined inclusion and exclusion criteria.
- Randomization Approach: Eligible participants will then be randomized into either the treatment or control group. This randomization is performed after the completion of the screening process and is based solely on the cancer type, ensuring an equal distribution of participants across different cancer categories within both groups.
- Implementation Details: The randomization process will be conducted using a computer-generated random allocation sequence to ensure impartiality and minimize selection bias.

- **Blinding and Unblinding**

- Efforts will be made to ensure that the trial intervention and control products are as indistinguishable as possible to maintain the integrity of blinding. This includes measures such as:
 - Standardization of software: Both the trial intervention and control software products will be delivered through the same app to minimize visual differences that could indicate the treatment assignment.

- Blinding of personnel: Personnel involved in the administration, assessment, and monitoring of participants will be blinded to the treatment assignment whenever possible. This includes investigators, outcome assessors, data analysts, and other relevant staff.

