- **Training Program for Live Coaches:** To ensure uniform delivery of the intervention across participants, live coaches will undergo a standardized training program. This program will cover the intervention's core components, ethical guidelines, communication skills, and use of the digital platform for interaction with participants. Regular refresher sessions and assessments will maintain coaching quality and consistency.

Ensuring Data Integrity and Consistency

- **Centralized Data Collection:** Utilizing a centralized digital platform for self-reported data and integrating EHR information will ensure data consistency and facilitate real-time monitoring of trial progress.
- **Standardized Assessments:** All assessments, including all the self-reported metrics, will be conducted following standardized protocols. Instructions on the timing and conditions of assessments will be clearly communicated to participants, and specialized training will be provided to any personnel involved in data collection or analysis.
- **Blinding Maintenance:** While blinding participants to the intervention details is not feasible, measures will be in place to ensure that data analysts and the Trial Monitoring Committee members are blinded to group assignments to minimize bias in outcome assessment and safety monitoring.

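### The Protocol calls the trial double-blind although its own Section 8 and the visible difference between the arms mean that participants cannot be blinded, and the primary endpoint is their self-report

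*Protocol*

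**What the plan says.** Three places in the Protocol present participants as blinded, or as approximately so.

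- 1.1, Blinding: "The study will be double-blind: Participants and the Principal Investigator will not be made aware of treatment assignment".
- 4.1, Method of Assignment: "The participants will not be aware if they are in control or test group".
- 6.6: "Efforts will be made to ensure that the trial intervention and control products are as indistinguishable as possible to maintain the integrity of blinding". It adds that personnel who administer, assess or monitor are to be blinded where possible.

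Section 8, under Blinding Maintenance, says otherwise: "While blinding participants to the intervention details is not feasible". It offers instead that data analysts and Trial Monitoring Committee members "are blinded to group assignments to minimize bias in outcome assessment and safety monitoring".

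The arms are described plainly. In the test arm (6.3), "Each session will be supervised live by a coactive coach for each participant". The control app (1.1) "Does not include live coaching and personalization".

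The primary endpoint is change in FACT-G, and 8.2 collects it as a score reported by the participant. Work motivation is also self-reported. Leave days and performance reviews may come from the employer or from the participant.

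The Combined protocol and SAP contains the same conflict between its 1.1, 4.1 and 6.6 and its Section 8, with FACT-G as a secondary endpoint there.

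**The concern.** A double-blind label tells a reader that knowledge of treatment could not have shaped the outcome. Here a participant either trains with a live coach several times a week or reads public guidance in an app, and then fills in the quality-of-life form. For FACT-G the participant is the outcome assessor. Blinding the analyst or the committee acts after the answer has been given and cannot remove an expectation effect from it.

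Two further passages raise the stakes. The rationale in 4.2 says that the design lets differences be attributed with greater certainty to the program's own components. Section 9.6 makes a significant improvement in quality-of-life scores a possible ground for early stopping, so the same unprotected measurement could feed a decision to end the trial. No passage names unblinded self-report as a limitation of the FACT-G comparison.

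**Working it through.** **Step 1. Who is blinded, by role, as the Protocol has it.**

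- *Participants:* unaware according to 1.1 and 4.1; products as alike as possible in 6.6; blinding to the intervention details not feasible in Section 8.
- *Coaches:* covered by the 6.6 wording on personnel who administer, but only the test arm has coaches, so a coach knows the arm of everyone coached.
- *Principal Investigator:* blinded in 1.1; where possible in 6.6. In 9.6 the trial team stays blinded, yet the Principal Investigator is consulted on stopping on the basis of interim findings.
- *Data analysts:* blinded in 6.6 (where possible) and in Section 8; in 9.6 those analysing the data may see unblinded data.
- *Trial Monitoring Committee:* blinded in Section 8; in 9.6 it reviews interim results and recommends stopping or continuing.

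The statements on participants conflict directly. Those on the other roles do not add up to one clear position.

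**Step 2. Which outcomes are exposed (8.2).** FACT-G and motivation: always, because both are self-reported. Leave days and performance scores: only where self-report is used instead of employer records.

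**Step 3. Basis for an illustration.** Inputs from 9.7: FACT-G 70 against 85 (difference 15), spread 20 (labelled a variance), alpha 0.05, power 80%, one-tailed, 1:1, 21 per arm; 146 randomized, 102 left after 30% dropout, so 51 per arm.

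Reproducing the plan's FACT-G figure, with n per arm = 2 × (z_alpha + z_power)² × (SD/difference)²:

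- 20 as an SD, one-sided: 2 × (1.645 + 0.842)² × (20/15)² = 21.98, so 22 per arm against 21 stated.
- 20 as an SD, two-sided: 27.9, so 28 per arm.
- 20 as a true variance (SD = √20 = 4.47), one-sided: 2 per arm.

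Only the first comes close, so 20 is read as an SD below. Dropout: 102/0.70 = 145.7, so 146, as stated.

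**Step 4. Illustration.** The documents give no expectation effect. Assume a shift b of 2 to 4 FACT-G points and no true effect.

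SE = 20 × √(2/51) = 3.96.

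One-sided rejection = 1 − Φ(1.645 − b/SE). Two-sided rejection = 1 − Φ(1.960 − b/SE) + Φ(−1.960 − b/SE).

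| b (points) | b/SE | one-sided 5% test | two-sided 5% test |
|---|---|---|---|
| 0 | 0 | 5.0% | 5.0% |
| 2 | 0.51 | 12.7% | 8.0% |
| 3 | 0.76 | 18.7% | 11.8% |
| 4 | 1.01 | 26.3% | 17.3% |

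For b from 2 to 4 with other SDs and 51 per arm: SD 15 gives 16.6% to 38.3% one-sided and 10.3% to 27.0% two-sided; SD 25 gives 10.7% to 20.1% and 6.9% to 12.7%.

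**The case against.** **The passages might be about different things.** Section 8 speaks of intervention details, while 1.1 and 4.1 speak of assignment and group. With an active comparator in the same app, a participant could know the content received without being told which arm is under test. This is the best defence, but it does not hold. No section describes hiding the hypothesis, 10.3 promises participants an explanation of the trial's purpose and procedures, and the presence or absence of a coach makes the arm easy to infer. Even with the label hidden, expectation follows from knowing the treatment received.

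**A reader might infer that the Protocol credits FACT-G with protection by participant blinding.** The documents do not support that. No sentence says so, the primary analysis in 9.2 does not mention blinding, and Section 8 partly discloses the problem. What stands is narrower: the label is wrong, and the safeguard that Section 8 offers for outcome assessment does not reach a questionnaire completed by the participant.

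**A reader might infer that all the work outcomes are self-assessed.** They are not necessarily: employer records are an allowed source for leave days and performance scores.

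**A reader might take the rejection rates as an estimate of bias in this trial.** They are not one. The shift is assumed, similar arithmetic applies to any unblinded self-report comparison, and rewording the label does not change it. The calculation is a plain two-sample test on 51 completers per arm, whereas 9.1 and 9.2 plan an MMRM with multiple imputation on all randomized participants.

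**A few points might seem minor beside a planned effect of 15.** But an observed difference of 1.645 × 3.96 = 6.5 points already reaches one-sided significance, and 2 to 4 points is 31% to 61% of that (2/6.5 and 4/6.5).

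**Participants cannot be blinded to live coaching.** Agreed. The criticism is of the claim to blind them, not of the lack of blinding.

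**Conclusion.** The point holds as an internal contradiction about a stated design property. Sections 1.1 and 4.1 claim that participants are blinded; Section 8 and the description of the arms show that they are not. It reaches the primary endpoint because FACT-G is self-reported, and it reaches early stopping through 9.6. It does not show that the FACT-G comparison is biased by any known amount, and it changes no sample size. The range of about 8% to 17% two-sided, or 13% to 26% one-sided, is an illustration that depends on three assumptions: a shift of 2 to 4 points, an SD of 20 in place of the variance printed in 9.7, and a simple test on 51 completers per arm. What can be said without those assumptions is that a positive FACT-G result may contain an expectation effect that this design cannot separate from benefit. It should not be presented as double-blind evidence.

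**What to change.** Make these changes in the Protocol, and in the matching sections of the Combined protocol and SAP if that document remains in use.

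1. In 1.1, remove the term double-blind and the claim that participants are unaware of assignment.
2. In 4.1, delete the sentence "Blinding: The participants will not be aware if they are in control or test group".
3. In 6.6, remove the implication that participants and coaches are blinded. Delivery through the same app can stay as a description.
4. Put one role-by-role statement in their place, and reconcile 1.1, 4.1, 6.6, Section 8 and 9.6 with it. Participants and coaches: not blinded. Principal Investigator, data analysts and Trial Monitoring Committee: the status of each stated explicitly, with the exception in 9.6 that those doing interim analyses may see unblinded data.
5. In 8.2 or 9.2, state that FACT-G is an unblinded self-report. Add that a positive result, including one used for early stopping under 9.6, may contain an expectation effect and will not be reported as double-blind evidence. Say the same for motivation, and for leave days and performance scores where self-report is the source.

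The cost is protocol wording. Sample size, procedures and analysis model are unchanged. The design is described less favourably, and the conclusion that the trial can support is narrower.
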